9.1.4 Pooling

No Data pooling will be performed.

9.1.5 Unscheduled Measurements

Unscheduled measurements will be included in the listings. With the exception of unscheduled measurements used for baseline, unscheduled measurements will be excluded from the descriptive statistics and statistical analysis.

In case an unscheduled measurement was performed immediately after the scheduled measurement because of a previous measurement error (e.g. equipment failure), this repeated measurement will be used, and the original erroneous measurement will be excluded from the analysis.

9.2 Analysis Data Definitions

9.2.1 Baseline Definition

Unless otherwise stated, baseline for post-dose evaluations is defined as the last observation recorded before the study drug administration. The last observation can be an unscheduled / repeated measurement.

9.2.2 Treatment/Subject Grouping

Assignment of subjects to a hepatic function group will be based on the Child-Pugh score at Screening.

Label	Grouping
IMP	Apaglutide (TA799): a single 5 mg dose of apaglutide administered by subcutaneous (SC) injection to the abdomen.
Hepatic Function Group	Cohort 1: moderate hepatic impairment (Child-Pugh B score 7 – 9 points) Cohort 2: normal hepatic function Cohort 3: mild hepatic impairment (Child-Pugh A score 5 – 6 points)

The Child-Pugh score will be determined as follows:

Child-Pugh Score	Point Scored for observed Findings		
	1 point	2 points	3 points
Encephalopathy grade*	0	1 or 2	3 or 4
Ascites	Absent	Slight	Moderate
Serum bilirubin (mg/dL)	<2.0	2 – 3	>3
Serum Albumin (g/dL)	>3.5	2.8 – 3.5	<2.8
Prothrombin time, sec prolonged	<4	4 – 6	>6

*Grade 0: normal consciousness, personality, neurological examination, electroencephalogram.
 Grade 1: restless, sleep disturbed, irritable/agitated, tremor, impaired handwriting, 5 cps waves.
 Grade 2: lethargic, time-disoriented, inappropriate, asterixis, ataxia, slow triphasic waves.
 Grade 3: somnolent, stuporous, place-disoriented, hyperactive reflexes, rigidity, slower waves.
 Grade 4: unrousable coma, no personality/behavior, decerebrate, slow 2-3 cps delta activity.

9.2.3 Common Variable Derivations

Variable	Data Type	Definition/Calculation
Change from Baseline	All	Post-dose Observation minus Baseline Observation
Analysis Study Day (Prior to Dose)	All (except ADPP)	Date of Measurement minus Dose Date
Analysis Study Day (Post Dose)	All (except ADPP)	Date of Measurement minus Dose Date +1

9.2.4 QC

The analysis datasets and the TFLs will be QC'd according to the PRA QC plan.

9.2.4.1 Critical Data

The QC plan requires datasets to be classified as critical or non-critical. As the primary objective of this study is to characterize the pharmacokinetics the datasets considered critical are subject level, and pharmacokinetic (ADSL, ADPC, and ADPP). As these are related to the primary objectives these datasets will be double programmed per the QC Plan.

Table 2 ADaM Datasets

ADaM Dataset Name	Description
ADSL	Subject-Level Analysis Dataset

ADaM Dataset Name	Description
ADAE	Adverse Events Analysis Dataset
ADEG	ECG Analysis Dataset
ADLB	Laboratory Test Results Analysis Dataset
ADPC	Pharmacokinetic Concentrations Analysis Dataset
ADPP	Pharmacokinetic Parameters Analysis Dataset
ADVS	Vital Signs Analysis Dataset

9.2.5 ADaM Datasets and Metadata

The analysis datasets will be generated in accordance with Clinical Data Interchange Standard Consortium (CDISC) Analysis Data Model (ADaM) Version 2.1.

ADaM compliant datasets will be delivered to the sponsor. A define.xml file version 2 with the corresponding metadata will be included. Analysis results metadata are excluded.

9.3 Software

The statistical analysis and reporting will be done using [SAS®](#) for Windows™ Version 9.4 or higher (SAS Institute, Inc.).

PK parameter calculations will primarily be done using [Phoenix® WinNonlin®](#) version 8.1 or higher (Certara, USA, Inc.) Additional PK computations may be performed in [SAS®](#).

9.4 Statistical Methods

9.4.1 Statistical Outlier Determination

No statistical outlier analysis is planned.

9.4.2 Predetermined Covariates and Prognostic Factors

There are no predetermined covariates or prognostic factors.

9.4.3 Hypothesis Testing

No formal hypothesis testing will be done.

9.5 TFL Layout

The layout of Tables, Figures and Listings (TFLs) will be according to the ICON IEB (former PRA EDS) standards.

Table shells are provided with and approved as part of this SAP. Small changes to shell layout due to the nature of the data may be required after lock at the discretion of the ICON lead biostatistician. Other changes to the shells may be out of scope. The TFLs will be provided as a single document in Adobe PDF format (in A4 format), and as individual files for each table, figure and listing in Rich Text Format (.rtf).

Format:

- Page size: A4
- Data in listings will be sorted by hepatic function group, subject number and time point.
- Data in tables will be sorted by hepatic function group and time point.

- Column titles will be in title case letters.
- All tables and listings will be in landscape format.
- The following hepatic function group labels will be used in the TFLs:
 - Normal
 - Mild
 - Moderate

10.0 Analysis Sets

Analyses	Enrolled Set	Safety Set	Pharmacokinetic Concentrations Set	Pharmacokinetic Parameter Set
Disposition Summaries	✓			
Safety Assessments		✓		
Baseline Characteristics		✓	Demographic summary (if not identical to Safety Set)	Demographic summary (if not identical to Safety Set)
PK Concentrations			✓	
PK Parameters				✓

10.1 Enrolled Set

The enrolled set will consist of subjects who signed the ICF for the study. This includes subjects who are considered screen failures. For these subjects a limited amount of data will be included in the Study Data Tabulation Model (SDTM). This set will be used for disposition summaries.

10.2 Safety Set

The Safety Analysis Set (SAS) comprises all subjects who have received at least one dose of IMP (apaglutide).

All safety analyses will be based upon the Safety Analysis Set.

10.3 Pharmacokinetic Concentrations Set

The PK Concentration Set (PKCS) is a subset of subjects in the SAS who have had at least one PK sample collected.

All PK concentration summaries will be conducted using the PKCS.

10.4 Pharmacokinetic Parameter Set

The PK Parameter Set (PKPS) is a subset of subjects in the SAS who have had at least one PK parameter of interest estimated.

All PK parameter summaries and primary analysis will be conducted using the PKPS.

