5.2. Number of Subjects

A total of approximately 16 to 32 subjects will be enrolled. In Part 1, approximately 16 subjects will be enrolled; approximately eight subjects with moderate hepatic impairment (Child-Pugh B; Cohort 1) and approximately eight subjects with normal hepatic function (Cohort 2) to ensure at least six evaluable subjects in each group. Subjects with normal hepatic function will be matched 1:1 for age (± 10 years), BMI ($\pm 15\%$), and sex (1:1) to subjects with moderate hepatic impairment.

If the decision criterion to proceed to Part 2 is met, approximately eight subjects with mild hepatic impairment (Child-Pugh A; Cohort 3) will be enrolled to ensure at least six evaluable subjects in each group. The matching will be a group matching for age, BMI, and sex, with approximately 50% of the subjects with normal hepatic function (Cohort 2) on both sides of the median for age and BMI of all subjects with hepatic impairment (Cohorts 1 and 3), and with approximately the same sex distribution of the normal hepatic function subjects (Cohort 2) as compared with all subjects with hepatic impairment (Cohorts 1 and 3). As many as possible of the matching controls enrolled into Part 1 will serve as matching controls for Part 2. Additional subjects with normal hepatic function may be enrolled in order to meet the given matching criteria when the last PK sample of the last subject with hepatic impairment has been taken.

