16.1.1.2 Parameters

- PK Parameters for apaglutide as defined in [Table 3: Plasma Parameters](#).

Table 3: Plasma Parameters

Parameter	Description	SAS Programming Notes
C_{max}	Maximum plasma concentration. Observed peak analyte concentration obtained directly from the experimental data without interpolation, expressed in concentration units	Cmax from WNL
AUC_{last}	Area under the concentration-time curve (time 0 to time of last quantifiable concentration).	AUC_{last} from WNL
AUC_{inf}	Area under the plasma concentration-time curve (time 0 to infinity). calculated as: $AUC_{0-inf} = AUC_{0-last} + (C_{last}/k_{el})$ where C_{last} is the observed concentration at the last time point with concentrations above the lower limit of quantification (LLOQ).	AUC_{inf_obs} from WNL If $AUC_ \%Extrap_obs > 20\%$ then parameter is flagged
AUC_{0-168h}	Area under the plasma concentration-time curve from time 0 to 168 hours post-dose.	AUC_{0-168} from WNL where partial time =168
t_{max}	Time to maximum plasma concentration. First observed time to reach peak analyte concentration obtained directly from the experimental data without interpolation, expressed in time units.	T_{max} from WNL
k_{el} (also denominated as λ_z)	Terminal phase rate constant calculated by linear regression of the terminal log-linear portion of the concentration vs. time curve. Linear regression of at least three points and an adjusted r^2 greater than or equal 0.80 are required to obtain a reliable k_{el} .	$\Lambda_{z_}$ from WNL If adjusted $Rsq < .80$ then parameter is flagged
$t_{1/2}$	Terminal phase half-life expressed in time units. Adjusted r^2 greater than or equal to 0.80 is required to obtain a reliable $t_{1/2}$.	HL_{Λ_z} from WNL If adjusted $Rsq < .80$ then parameter is flagged
CL/F	Apparent total clearance of the drug from plasma after subcutaneous administration	CL_F_obs from WNL
Vz/F	Apparent volume of distribution during the terminal phase after subcutaneous drug administration	Vz_F_obs from WNL

The PK parameters below will be listed only.

%AUCextra	Percentage of AUC_{0-inf} that is due to extrapolation from the time of last observed concentration to infinity.	$AUC_ \%Extrap_obs$ from WNL
Adj r^2	Goodness of fit statistic for the loglinear terminal elimination phase of the concentration time profile identified by least squares linear regression and adjusted	$Rsq_adjusted$ from WNL

	for the number of points (minimum of 3, excluding C_{max}) used in the estimation of K_{el}	

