16.2.2.1 Statistical Analyses

Part 1:

Analysis of variance (ANOVA) will be used to compare the natural log transformed AUCinf or AUClast (if AUCinf cannot be calculated) and Cmax for apraglutide between normal hepatic function group (Reference) and the moderate impaired hepatic group (Test).

If there is a dropout in the moderate hepatic function group, the “matched” subject in the normal hepatic function group will be excluded from this analysis. The subject from the normal hepatic group may however be used in the analysis for part 2 if there is a matched Mild hepatic function group subject.

If the AUCinf is extrapolated by more than 20% for 1 subject, the AUClast should be used for all subjects for the determination of the Geometric Mean Ratio (GMR).

Estimates of the mean differences (Test-Reference) and corresponding 90% CIs will be obtained from the model. The mean differences and 90% CIs for the differences will be exponentiated to provide estimates of the GMR (Test/Reference) and 90% CIs for the ratios.

The following SAS PROC MIXED pseudo-code may be used:

```
proc mixed data = adpp;
  by parameter;
  class hepatic_group;
  model log(aval) = hepatic_group;
  lsmeans hepatic_group / cl alpha = 0.1;
  estimate "Moderate hepatic impairment vs Normal hepatic function"
hepatic_group 1 -1 /e cl alpha=0.1;
run;
```

Part 2 (if conducted):

Part 2 may be conducted if apraglutide AUCinf (or AUClast when AUCinf cannot be calculated) GMR for the moderate hepatic impairment group versus the normal group is ≥ 2 .

Analysis of variance will be used to compare the natural log transformed AUCinf or AUClast and Cmax for apraglutide between normal hepatic function group from Part 1 (Reference) and the mild impaired hepatic group (Test). Estimates of the mean differences (Test-Reference) and corresponding 90% CIs will be obtained from the model. The mean differences and 90% CIs for the differences will be exponentiated to provide estimates of the GMR (Test/Reference) and 90% CIs for the ratios.

The following SAS PROC MIXED pseudo-code may be used:

```
proc mixed data = adpp;
  by parameter;
  class hepatic_group;
  model log(aval) = hepatic_group;
  lsmeans hepatic_group / cl alpha = 0.1;
  estimate "Mild hepatic impairment vs Normal renal function" hepatic_group
1 -1 /e cl alpha=0.1;
run;
```

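### No rule keeps a normal-group dropout's incomplete PK profile out of the primary AUC comparison, and that profile can move every subject to AUClast

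*SAP*

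**What the plan says.** **Who is analysed.** The PK Parameter Set (PKPS) is the "subset of subjects in the SAS who have had at least one PK parameter of interest estimated" (SAP 10.4; Protocol 12.3.1.3 agrees). The SAP adds: "All PK parameter summaries and primary analysis will be conducted using the PKPS".

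**What AUClast is.** SAP Table 3 (16.1.1.2) runs it from "time 0 to time of last quantifiable concentration". It has no fixed end time, so for a dropout it ends at the last sample before leaving.

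**When the metric changes.** SAP 16.2.2.1: "If the AUCinf is extrapolated by more than 20% for 1 subject, the AUClast should be used for all subjects". SAP 7.2 has the same rule for the Part 1 interim, whose GMR decides on Part 2. SAP 16.2.2 flags profiles with more than 20% extrapolation or adjusted r² below 0.80 and keeps them in the descriptive statistics. It has no rule on the ANOVA.

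**When AUCinf is missing.** The ANOVA compares "natural log transformed AUCinf or AUClast (if AUCinf cannot be calculated) and Cmax". The text does not say whether AUClast then replaces AUCinf for that one subject or for all.

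**Dropouts.** The one rule in SAP 16.2.2.1 begins "If there is a dropout in the moderate hepatic function group" and removes the matched normal subject. What happens to the dropout's own data is not written, and dropout is not defined. Nothing covers a dropout in the normal group or, in Part 2, the mild group. SAP 7.2 has no dropout rule.

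**Evaluability.** Protocol 5.2 enrols about eight per group "to ensure at least six evaluable subjects in each group", but neither document defines evaluable, and the PKPS does not use the term. The sponsor may replace non-evaluable subjects, but replacement is not said to remove the first subject's record from the PKPS.

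**The concern.** AUC over unequal intervals is not a comparable measure of exposure. Suppose a control leaves after a few days. There is a Cmax and an AUClast, so the subject is in the PKPS. If a terminal slope can be fitted, the short profile will usually extrapolate more than 20%, and the rule then puts all subjects on AUClast. The ANOVA now compares one control's AUC over a few days with AUC to as late as 312 h in the rest. The reference geometric mean falls and the GMR rises toward 2.0, the value that opens Part 2.

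A mild-group dropout in Part 2 would have the opposite effect: that group's exposure would be understated. This assumes that the switch, written under Part 1, carries over to Part 2.

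If too few points follow the peak for a slope, there is no AUCinf and no extrapolation percentage. The unclear fallback then applies. Read per subject, it sets one subject's AUClast against the others' AUCinf, which is the same mismatch by another route.

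**Working it through.** The plan gives no power calculation, variability, half-life or dropout rate, so there is no figure of its own to reproduce. The check models one truncated control.

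**From the documents:** sampling at 0, 6, 12, 24, 28, 36, 40, 48, 60, 72, 96, 120, 144, 168, 240 and 312 h; linear-up/log-down AUC; at least 3 points for the slope, excluding Cmax; 8 per group, at least 6 evaluable; threshold 2.0; 90% CI.

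**Assumed, not in the documents:** one-compartment SC profile, C(t) ∝ exp(−kt) − exp(−kₐt), with absorption half-life 12 h and elimination half-life 24 to 100 h; all samples quantifiable; slope from the last 3 points.

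**Formulas.** f = AUClast at the last sample ÷ AUC0-312. The GMR is a ratio of geometric means, so one truncated control among n multiplies it by f^(−1/n). Extrapolation = (C_last/k_el) ÷ (AUClast + C_last/k_el).

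**Results for a true GMR of 2.0, n = 8, one control truncated:**

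| Half-life | f, 72 h | Extrap. | GMR | f, 168 h | Extrap. | GMR |
|---|---|---|---|---|---|---|
| 24 h | 0.764 | 27% | 2.07 | 0.985 | 2% | 2.00 |
| 36 h | 0.633 | 42% | 2.12 | 0.944 | 6% | 2.01 |
| 50 h | 0.527 | 55% | 2.17 | 0.887 | 13% | 2.03 |
| 72 h | 0.427 | 68% | 2.22 | 0.809 | 24% | 2.05 |
| 100 h | 0.357 | 78% | 2.27 | 0.742 | 36% | 2.08 |

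Example: 2.0 × 0.527^(−1/8) = 2.0 × 1.083 = 2.17. With 6 per group the 72 h column runs from 2.0 × 0.764^(−1/6) = 2.09 to 2.0 × 0.357^(−1/6) = 2.37.

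**Does the switch fire?** At 72 h, yes in every row. At 168 h, only at the 72 h and 100 h half-lives. In the other rows AUCinf is kept, so 2.00 to 2.03 would arise only if something else forced AUClast. Completers to 312 h extrapolate 0% to 13% in this model, so without the dropout the analysis would stay on AUCinf.

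**Fallback route.** At a 50 h half-life and last sample 48 h, only two points follow the peak (36 h), so there is no slope. AUC to 48 h is 0.340 of the completers' AUCinf. If AUClast were substituted for that control alone, a true 2.0 would read 2.0 × 0.340^(−1/8) = 2.29.

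**Effect on the decision.** Take f = 0.4 and an assumed between-subject CV of 30%. The log shift is −ln(0.4)/8 = 0.115. The log SD is √ln(1.09) = 0.294, and the SE of the difference is 0.294 × √(2/8) = 0.147. At a true 2.0, P(GMR ≥ 2) = Φ(0.115/0.147) = Φ(0.78) ≈ 0.78, against 0.50 without truncation. Simulation gave 0.79, and 0.73 to 0.88 across CV 40% to 20%.

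**The case against.** Several points on the other side stand.

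- **Moderate-group dropouts.** A reader might infer that the SAP keeps a moderate dropout's truncated AUC while discarding the complete control. That would bias the GMR down and could stop the trial wrongly. The documents do not support this. Removing the matched control makes sense only if the dropout goes too, so the rule implies pair deletion. The fault there is unclear, one-sided wording.
- **Early exit is unlikely.** Subjects stay in the unit for the first 8 days (Protocol 4.1.3), which covers sampling to 168 h. Missing the Day 11 and Day 14 visits is the more plausible loss, and its effect is small.
- **The switch is conditional.** A reader might infer that any dropout triggers it. Later dropouts often stay under 20%, and very early ones may have no percentage at all.
- **Part 2 is not automatic.** SAP 7.2 says only that it may be conducted, and the interim report includes raw concentrations, where a short profile would be visible.
- **The half-life is assumed.** Shorter values shrink the effect, as the table shows.

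These points limit the likelihood and size. They do not supply a rule for a normal-group dropout, and spotting the problem after seeing the interim data is weaker than a rule set in advance.

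**Conclusion.** The gap is real and should be closed, within limits. It holds in full for a normal-group dropout with an estimable slope and more than 20% extrapolation. Followed as written, the SAP keeps that subject in the ANOVA and moves everyone to AUClast, which raises the GMR. The mild group in Part 2 also has no dropout rule. For the moderate group the intent is probably right but needs stating. The AUClast fallback is ambiguous in all groups.

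For one control last sampled at 72 h, the shift is about 3% to 14% on the ratio (2.07 to 2.27 for a true 2.0, 8 per group). For one last sampled at 168 h it is at most 4%. This changes the decision only when the estimate lies near 2.0. All sizes rest on the assumed half-lives, absorption rate and CV. The gap in the rules does not.

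**What to change.** In SAP 7.2, 10.4 and 16.2.2.1:

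1. Define dropout. State that a dropout with an incomplete profile is excluded from the AUCinf/AUClast ANOVA, and apply one dropout/pair rule to all groups, at the interim and the final analysis. For Part 2, say what counts as the match, because Protocol 5.2 matches by group there.
2. Admit a subject to the AUCinf comparison if AUCinf is reliable (adjusted r² at least 0.80, extrapolation at most 20%), whatever the last sampling time. Admit a subject to an AUClast comparison only if sampled to 312 h or to a result below the quantification limit. Requiring 312 h for AUCinf as well would discard good data: at a 50 h half-life, a subject last sampled at 240 h extrapolates only about 5%.
3. State that a profile shortened by dropout or missed visits cannot change the metric for other subjects, and that any fallback to AUClast applies to all subjects.
4. If an AUC over observed time is needed, use one common interval. Add AUC0-168h, already a primary endpoint (SAP 5.1.1) but absent from the ANOVA and the interim table, for subjects sampled to 168 h.

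**Cost:** a few lines of SAP text, and the loss of an incomplete subject and its match from the AUC comparison. In simulation at CV 30%, going from 8 v 8 to 7 v 7 widened the median ratio of upper to lower 90% limit from 1.66 to 1.72. Keeping a truncated value (f = 0.4) gave 1.90. Removing the pair returned P(GMR ≥ 2) at a true 2.0 to 0.50.

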11.0 Subject Disposition

The number and percentage of subjects enrolled, dosed, and members of each analysis set will be presented. The number and percentage of subjects who withdrew from the study prematurely and a breakdown of the corresponding reasons for withdrawal will also be presented for both the dosed subjects and screen failures.

12.0 Protocol Deviations

Protocol deviations will be listed by subject.

13.0 Demographic and Baseline Characteristics

13.1 Demographics

All demographic data collected during the screenings visit will be listed by subject.

Subject demographics will be summarized descriptively for all subjects by hepatic function group and overall. The summary will include the subjects' age (in years), sex, race, ethnicity, weight (in kg), height (in cm), and BMI (in kg/m²). For female subjects the childbearing potential will be listed as well.

Demographics will be summarized for the safety, PK concentrations and PK Parameter analysis sets, if they are different from one another.

13.2 Medical History

Medical history, categorized by preferred term according to the latest version of Medical Dictionary for Regulatory Activities (MedDRA), will be listed by subject.

13.3 Other Baseline Characteristics

Substance use (tobacco and alcohol) will be listed.

The results of drug and alcohol screen will be listed.

Non-compliance to in- or exclusion criteria (if any) will be listed.

The Child-Pugh Assessment Results will be listed.

Serology results will be listed.

SARS-CoV-2 Results will be listed.

Results for pregnancy, FSH and estradiol will be listed (females only, if required)

14.0 Concomitant Medications

Concomitant medication will be listed. Medications with an end date prior to the first dose of study drug will be considered prior medications and will be noted in the listing. If a partial date allows a medication to be considered concomitant it will be categorized as such. Concomitant medications will be coded by using World Health Organization Drug Dictionary.

15.0 Treatment Compliance and Exposure

Exposure data will be listed by subject.

16.0 Pharmacokinetic Analyses

16.1 Pharmacokinetic Variables

PK concentrations will be collected in plasma and will be analyzed by Altasciences Bioanalysis and Research Services.

